Official Title: The Effect of Dental Anxiety on the Success of Mandibular Anesthesia in Mandibular Molar Teeth with Symptomatic Irreversible Pulpitis: A Prospective Clinical Study

NCT Number: Not available

Date: 15/12/2024

Null Hypothesis (H₀): Dental anxiety does not affect the success of mandibular anesthesia in the treatment of symptomatic irreversible pulpitis in mandibular molar teeth.

Study arms: A prospective clinical trial with two parallel intervention arms. Participants will be divided into two groups based on their Modified Dental Anxiety Scale (MDAS) scores:

- Group 1 (Low Anxiety Group): MDAS score < 10
- Group 2 (Moderate to High Anxiety Group): MDAS score ≥ 11 (including those with dental phobia if MDAS > 19)

Sample Size Calculation: Using G*Power 3.1.9.7 software, based on an effect size of 0.8, $\alpha = 0.05$, and power = 0.80, the required sample size was determined as **26 patients per group**, totaling **52 participants**. The actual power achieved was 81%.

Materials and Methods:

Inclusion Criteria:

- Systemically healthy adults aged 18–65
- Mandibular molar teeth with symptomatic irreversible pulpitis requiring root canal treatment
- Radiographic evidence of closed apex and absence of periapical pathology
- Periodontal probing depth ≤ 3 mm
- Tooth mobility < 0.5 mm
- Pain score of 55–170 mm on the Heft-Parker Visual Analog Scale (HP-VAS) (i.e., moderate or severe pain)
-

• Exclusion Criteria:

- Systemic disease
- Teeth with open apex, periapical lesion, internal or external resorption
- Periodontal probing depth > 3 mm
- Tooth mobility > 0.5 mm
- HP-VAS score < 55 mm (no or mild pain)
- Pregnant patients or those with allergy to articaine

Procedure:

- All treatments and measurements will be conducted between 09:00 and 12:00 to minimize circadian and cortisol fluctuations.
- Patients will avoid food intake for at least 2 hours before treatment and abstain from caffeine, alcohol, tobacco, and intense exercise within 24 hours.
- Patients will rest in the dental chair for 5 minutes, then their demographic data will be recorded.
- MDAS will be administered to assess anxiety level.
- HP-VAS will be used to assess pre-treatment pain level.
- Pulse rate, SpO₂, and salivary cortisol levels will be recorded pre- and post-anesthesia.

Anesthesia Protocol:

- All procedures are performed by a single operator in a one-unit room.
- Topical anesthesia: 10% lidocaine spray (Locanest) applied for 60 seconds.

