- IANB (Inferior Alveolar Nerve Block):
 - 1.8 ml of 4% articaine hydrochloride with 1:100,000 epinephrine (Ultracaine DS Forte) via 27G needle
- Buccal and lingual infiltration:
 - Additional 1.8 ml injection performed 5 minutes after IANB
- Block Failure Definition:
 - If deep lip numbness is not achieved within 15 minutes, the block is considered failed and the participant is withdrawn from the study.

Outcome Evaluation:

- During treatment, if the patient feels pain, they raise their hand, and the pain is marked on the HP-VAS.
- If required, supplemental anesthesia (PDL or intrapulpal) will be administered and recorded.
- Successful anesthesia: No or mild discomfort
- Failed anesthesia: Moderate or severe pain
- Cold test will be performed 15 minutes after IANB. If positive, additional anesthesia will be given.

Biological Sampling:

- Saliva samples will be collected 15 minutes before and after anesthesia.
- Samples will be stored at -80°C until analysis.
- Special sterile, single-use Sali-Tubes (SLV-4158, DRG, Germany) will be used.

Statistical Analysis:

All statistical analyses will be performed using SPSS Statistics 20 software (IBM Corp., Armonk, NY) at a 5% significance level. If the data are normally distributed, Student's t-test will be used to compare preoperative pain levels, salivary cortisol, SpO₂, and pulse rate across different anxiety levels. Chi-square test will be used to analyze the relationship between anxiety levels and the success rate of anesthesia.

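### Cortisol, pulse and SpO₂ are measured before and after anesthesia, but the named t-test does not state a time point and no planned analysis uses each patient's pre/post pair

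*Combined protocol and SAP*

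**What the plan says.** **Measurements.** The Procedure section has three physiological measures taken twice: "Pulse rate, SpO₂, and salivary cortisol levels will be recorded pre- and post-anesthesia". Biological Sampling gives the cortisol timing: "Saliva samples will be collected 15 minutes before and after anesthesia".

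**Analysis.** Statistical Analysis covers these measures in one sentence. It opens with a condition, "If the data are normally distributed", and continues: "Student's t-test will be used to compare preoperative pain levels, salivary cortisol, SpO₂, and pulse rate across different anxiety levels". The only other test in the plan is for the anesthesia outcome: "Chi-square test will be used to analyze the relationship between anxiety levels and the success rate of anesthesia".

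**Groups and hypothesis.** The groups are not randomised: "Participants will be divided into two groups based on their Modified Dental Anxiety Scale (MDAS) scores". The single stated null hypothesis is about anesthesia success: "Dental anxiety does not affect the success of mandibular anesthesia in the treatment of symptomatic irreversible pulpitis in mandibular molar teeth". The plan states no hypothesis on a physiological response.

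**The concern.** Each patient supplies a pre and a post value for three measures, but the one test named for them compares anxiety groups and does not say at which time point. The sentence allows at least three analyses: pre levels, post levels, or change. If the word for preoperative governs the whole list, the post values have no planned analysis at all. On any reading, no change score, paired test, group-by-time term or baseline adjustment is specified.

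This matters because of how the groups are formed. Patients sorted by an anxiety score may well differ in cortisol or pulse before anything is injected. A post-level difference then mixes two things: the anxious group starting at a different level, and the anxious group reacting differently to anesthesia. A reader of the trial report could take the first for the second. Leaving the time point open also allows the contrast to be chosen after the results are seen.

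**Working it through.** **Inputs from the document.** 26 patients per group; 5% significance level; effect size 0.8; stated achieved power 81%. The sidedness of the test and the outcome behind the effect size are not given. I take the test as two-sided and the effect size as a standardised mean difference.

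**Assumptions, not in the document.** Baseline gaps of 0.5 and 0.8 SD; a 0.5 SD difference in change; equal SD before and after and in both groups; pre-post correlation r from 0 to 0.8.

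**Step 1: reproduce the plan's own figure.** For a two-sample t-test with n per group, df = 2n − 2 and the noncentrality is d·√(n/2). At n = 26 and d = 0.8, df = 50 and the noncentrality is 0.8 × √13 = 2.88. The power is 0.8075, which matches the stated 81%; n = 25 gives 0.792. A one-sided test would need only 21 per group (0.817), so two-sided fits.

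**Step 2: post-level test when both groups change identically.** The post-anesthesia difference then equals the baseline gap, whatever r is.
- Gap 0.5 SD: noncentrality 0.5 × √13 = 1.80; the test is significant in 42% of trials.
- Gap 0.8 SD: noncentrality 2.88; significant in 81% of trials.

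A simulation of 20,000 trials with a 0.8 SD gap, no difference in change and r = 0.5 gave 81% for the post-level test and 5% for a test on change. In the same setting, separate pre and post tests disagreed on significance in 22% of trials. That pattern could itself be misread as a differential response.

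**Step 3: level tests when the response does differ.** With groups −0.4 SD apart before and +0.4 SD apart after (a 0.8 SD difference in change, r = 0.5), the pre and post tests each rejected in 29% of trials. The test on change rejected in 81%.

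**Step 4: precision of the change comparison.** SD of change = SD × √(2(1 − r)). For a true 0.5 SD difference in change, the standardised effect is 0.5 / √(2(1 − r)). With 26 per group:

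| r | √(2(1 − r)) | Standardised effect | Power |
|---|---|---|---|
| 0 | 1.41 | 0.35 | 24% |
| 0.2 | 1.26 | 0.40 | 29% |
| 0.3 | 1.18 | 0.42 | 32% |
| 0.5 | 1.00 | 0.50 | 42% |
| 0.7 | 0.77 | 0.65 | 63% |
| 0.8 | 0.63 | 0.79 | 80% |

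For comparison, a post-level test has 42% power for a 0.5 SD difference in response only if there is no baseline gap. With a 0.5 SD gap in the same direction, the post difference is 0.5 + 0.5 = 1.0 SD and the test is significant 94% of the time, but it is then testing a different quantity.

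**The case against.** The strongest reply is that the plan names no post-level test, so there is no wrong test to strike out. This stands. A between-group t-test on each patient's change would fit the wording, so a reader who infers that the plan commits to post levels, or that the t-test is incapable of addressing response, goes further than the text. The supportable defect is that the contrast is unspecified and the pairing unused.

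Second, the title and null hypothesis concern anesthesia success only. Describing levels at two time points, or checking that the anxiety grouping is reflected in stress markers, would be equally consistent with the sampling. This also stands: the documents do not say that the paired sampling was set up to test a differential response. It limits the importance of the point but does not remove it, because the post measurements are collected and will presumably be reported.

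Third, a reader might take the 42% and 81% as false-positive rates. They are not. If the groups differ after anesthesia, rejecting equal post levels is right. The fault would lie in interpreting that result as a response, and the documents do not themselves make that interpretation.

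Fourth, a change score is not always the more precise choice. Below r = 0.5 its SD exceeds that of a single level. In non-randomised groups, change-score analysis and ANCOVA also target different quantities, and neither is right by default. This is why change is proposed here as an addition with a stated target, not as a correction of an error.

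**Conclusion.** The point holds as a gap in specification for secondary measures. Three measures are taken twice, the only named test does not say which value it uses, and no planned analysis compares within-patient change between anxiety groups. A post-level comparison alone could not distinguish a pre-existing gap from a different response: with identical change and an assumed starting gap of 0.5 or 0.8 SD, it is significant in 42% or 81% of trials.

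Those figures rest on the assumed gaps, equal SDs and 26 analysed patients per group. The documents give no baseline difference and no pre-post correlation. The chi-square test of the null hypothesis and the sample size of 52 are unaffected. This is a cheap improvement worth making, not a threat to the trial's main conclusion.

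**What to change.** In Statistical Analysis:

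1. State that the Student's t-test for cortisol, pulse and SpO₂ compares pre-anesthesia levels between the two anxiety groups.
2. Add, for each measure, a between-group comparison of within-patient change (post minus pre), reported as an estimate with a 95% CI. With two time points this is equivalent to the group-by-time interaction.
3. Fix the scale for cortisol (raw or log) in advance. When baselines differ, equal absolute changes are unequal ratios, so the scale can decide whether a difference in change appears.
4. Report any comparison of post-anesthesia levels as descriptive, and do not interpret it as a response to anesthesia.

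**Cost.** A few sentences of text; no new patients, samples or software, and the change can be compared with the same t-test in SPSS. The downside is limited precision if the pre-post correlation is below 0.5: for a 0.5 SD difference in change, power is under 42% there and falls to 24% at zero correlation. The confidence interval should therefore carry the interpretation, and a non-significant result should not be read as equal response.

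### The MDAS score is obtained before anesthesia and nothing keeps it from the operator or the pain recorder, though the plan gives it no use before analysis

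*Combined protocol and SAP*

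**What the plan says.** All places are in the Combined protocol and SAP.

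- **Study arms:** "Participants will be divided into two groups based on their Modified Dental Anxiety Scale (MDAS) scores". Group 1 is below 10 and Group 2 is 11 or above.
- **Procedure:** after a short rest and the demographic questions, "MDAS will be administered to assess anxiety level". This comes before the Anesthesia Protocol. The administrator and the scorer are not named.
- **Anesthesia Protocol:** "All procedures are performed by a single operator in a one-unit room". A participant without adequate lip numbness at 15 minutes is withdrawn.
- **Outcome Evaluation:** "During treatment, if the patient feels pain, they raise their hand, and the pain is marked on the HP-VAS". Who makes the mark is not stated. The endpoint is defined by "Successful anesthesia: No or mild discomfort" and "Failed anesthesia: Moderate or severe pain". A cold test follows the block, and a positive result leads to more anesthetic. Separately, "If required, supplemental anesthesia (PDL or intrapulpal) will be administered and recorded", with no criterion and no named decision maker.

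MDAS does not appear among the inclusion or exclusion criteria, and no treatment step depends on it. No section mentions masking.

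**The concern.** Anxiety group is the exposure in the null hypothesis, and anesthesia success is the outcome compared by chi-square. If the people handling and recording the outcome know the exposure, any influence of that knowledge falls along the comparison being tested. Four steps after the MDAS are open to this:

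- the lip-numbness judgement, which decides who stays in the analysis;
- the reading of the cold test, which can lead to more anesthetic and so change later pain;
- how pain is prompted for and recorded on the HP-VAS;
- the use of supplemental anesthesia, which acts only indirectly because it is not part of the success definition.

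Since the score has no stated use before analysis, this exposure is avoidable. It cannot be undone once patients have been treated.

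**Working it through.** **1. Is the score needed before the outcome is recorded?** Eligibility does not use MDAS. The block, infiltration, cold test and supplement steps do not refer to it. Its only stated role is to form the groups. Enrolling to exactly 26 per group would need running scores, but the plan does not describe enrolment that way.

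**2. The plan's own figure.** Inputs from Sample Size Calculation: effect size 0.8, alpha 0.05, power 0.80. Reading these as a two-sided two-sample t-test with d = 0.8, the noncentrality is d × √(n₁n₂/(n₁+n₂)).
- 26 v 26: 0.8 × √(676/52) = 2.884, power 0.807.
- 25 v 25: 0.8 × √(625/50) = 2.828, power 0.791.

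So 26 per group and 81% reproduce.

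**3. What recording bias could do (illustration, assumed inputs).** The documents give no success rates. Let the true success rate p be the same in both groups (the null hypothesis), and let a share b of true successes in the anxious group be recorded as failures. The false-positive rate is the sum of Bin(x; 26, p) × Bin(y; 26, p(1−b)) over all tables whose uncorrected Pearson chi-square exceeds 3.841.

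| b | false-positive rate, p from 40% to 80% |
|---|---|
| 0 | 4.5% to 5.6% |
| 10% | 6.0% to 11.1% |
| 20% | 9.9% to 26.3% |
| 30% | 16.0% to 48.3% |

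This models one direction only, and no value of b can be taken from the documents.

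**4. How far single patients move the test (invented counts).** One patient is 1/26 = 3.8 points.
- 8/26 v 13/26 failures: 52 × (8×13 − 13×18)² / (26×26×21×31) = 1.997, p = 0.158.
- 8/26 v 16/26: 52 × (8×10 − 16×18)² / (26×26×24×28) = 4.952, p = 0.026.
- The same table with continuity correction: 52 × (208 − 26)² / 454,272 = 3.792, p = 0.052. Fisher's exact gives 0.050 (0.0505).
- One or two added failures do not cross 0.05 even uncorrected: 8 v 14 gives 0.092 and 8 v 15 gives 0.051.

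The plan names a chi-square test "at a 5% significance level" without saying whether it is corrected, so this example is fragile.

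**5. Cost of deferring the score (assumed splits).**
- Enrolling blind until both groups reach 26 overshoots. At a 50/50 split the expected excess is 52 × C(52,26)/2⁵² ≈ 6 patients. At 65/35 it is about 26/0.35 − 52 ≈ 22.
- Fixing the total at 52 instead, with 20 v 32: noncentrality 0.8 × √(640/52) = 2.807, power about 0.79. This refers to the t-test behind the sample size. The plan gives no power for the success comparison.

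**The case against.** The strongest reply is that much of the case rests on silence. A reader might infer that the single operator sees the MDAS result, takes the pain marks and decides on supplements. The documents do not say so: the MDAS and HP-VAS sentences are passive, and the single-operator sentence concerns procedures, which need not include questionnaires or pain marking. A room with one dental unit is not a room with one member of staff. This stands, and the supportable statement is that nothing prevents it.

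A reader might also infer that every one of these steps sets the endpoint. The written definition uses pain category only, and recording begins with the patient raising a hand. The cold test and supplements therefore act indirectly. Extra anesthetic given more readily to anxious patients could even lower their later pain, so the direction is open. This stands too.

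Last, a reader might infer that deferred scoring would largely remove the bias. Nothing supports that. It hides a number, while anxious behaviour stays visible and patients know their own anxiety.

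These replies limit how strongly the point can be put. They do not supply a reason for the score to be available before the outcome is recorded, or a safeguard against its being known.

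**Conclusion.** The point holds in a limited form. The plan obtains the grouping score before anesthesia, gives it no use until analysis, and masks neither the operator nor the pain recorder. Observer bias along the main comparison is therefore possible, and part of it is cheaply avoidable. Its size and direction cannot be found from the documents. The 6% to 26% range is conditional on assumed success rates of 40% to 80% and on 10% to 20% one-directional misrecording. It shows that the bias could matter, not that it is present. The shift from p = 0.158 to p = 0.026 should not be read as a likely effect, because it rests on invented counts and the uncorrected test.

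**What to change.** Before enrolment, amend the Procedure as follows:

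- The patient completes the MDAS form alone and seals it under a study number. It is opened and scored only after lip numbness (including any withdrawal), cold test, HP-VAS marks and any supplemental anesthesia have been recorded.
- The patient makes the HP-VAS mark. The plan names who scores the MDAS.
- The total stays at 52 and unequal groups are accepted, rather than enrolling until both reach 26.
- A score of 10, which now fits neither group, is assigned to one group in advance, so that no treated patient is unclassifiable.
- The remaining bias from visible anxiety and the patient's own reporting is stated as a limitation.

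The cost is a few sentences and some envelopes, with no added visit and no change to treatment. Unequal groups lose a little power, about two percentage points at 20 v 32 for d = 0.8, and more if the split is more extreme.

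### The only pain score planned during treatment is triggered by the patient's own hand signal, so measured anesthetic success depends partly on willingness to signal, which could differ by anxiety

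*Combined protocol and SAP*

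**What the plan says.** All references are to the combined protocol and SAP.

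- **Pain during treatment (Outcome Evaluation):** "During treatment, if the patient feels pain, they raise their hand, and the pain is marked on the HP-VAS". No other pain score during treatment is described.
- **Classification (same section):** "Successful anesthesia: No or mild discomfort" and "Failed anesthesia: Moderate or severe pain". No millimetre cut-off, time point or rule for patients who give no signal is attached to these definitions.
- **Pain score planned for everyone (Procedure):** "HP-VAS will be used to assess pre-treatment pain level". This is before treatment only.
- **Category boundary (Inclusion and Exclusion Criteria):** HP-VAS below 55 mm is no or mild pain, and 55 to 170 mm is moderate or severe pain. The boundary is given for eligibility and is not repeated for the outcome.
- **Related information (Outcome Evaluation):** "Cold test will be performed 15 minutes after IANB. If positive, additional anesthesia will be given", and "If required, supplemental anesthesia (PDL or intrapulpal) will be administered and recorded". Neither enters the definition of success or failure.
- **Groups (Study arms):** "Participants will be divided into two groups based on their Modified Dental Anxiety Scale (MDAS) scores".
- **Analysis (Statistical Analysis):** a chi-square test of success against anxiety level.

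**The concern.** A patient in moderate or severe pain who does not raise a hand has no score during treatment. The definitions need a pain category, and the only category available by default is no or mild discomfort. So a failure is observed only if two things happen: the pain occurs, and the patient signals it.

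In many trials this would add noise of much the same amount to each arm. Here the groups are formed by dental anxiety, and the null hypothesis is about anxiety. An anxious patient might signal sooner, or might stay silent to avoid an interruption or another injection. The documents exclude neither. Patients are not randomised to anxiety level, and no blinding of the operator to MDAS group is described. If signalling differs between the groups, that difference would be reported as a difference in anesthetic success, or would mask a real one.

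**Working it through.** **Inputs from the plan.** 26 patients per group, 5% significance level, chi-square test. The stated pair of 26 per group and 81% power is reproduced by a two-sample, two-sided t-test with effect size 0.8, which gives 80.7% at n = 26. That calculation does not concern the success rate; I take only the 26 from it.

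**Inputs assumed.** The documents give neither true failure rates nor signalling rates. Let f be the true probability of moderate or severe pain in a group, and s the probability that a patient with such pain signals it. If silent patients count as successes:

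- observed failure = f × s
- with the same f in both groups, false difference = f × (s₁ − s₂)

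Rejection probabilities come from exact binomial enumeration of the uncorrected Pearson chi-square test at 26 v 26.

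**1. No true difference.** f = 40% in both groups, signalling 95% v 75%.
- Observed failure: 0.40 × 0.95 = 38% and 0.40 × 0.75 = 30%.
- Rejection: 10.1%, against 5.3% with full signalling. Swapping the groups reverses the direction and leaves the rejection rate unchanged.

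**2. True difference, anxious group signals less.** f = 30% (low anxiety) v 60% (anxious). With full signalling the difference is 30 points and power is 58.3%. With 80% signalling in the anxious group, its observed failure is 0.60 × 0.80 = 48%, and:

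| Signalling, low-anxiety group | Observed failure, low-anxiety group | Difference | Power |
|---|---|---|---|
| 100% | 30% | 18 points | 27% |
| 95% | 28.5% | 19.5 points | 32% |
| 90% | 27% | 21 points | 36% |

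**3. The bias can run either way.** With f = 30% v 70%, power is 82.8% under full signalling. It falls to 47.5% if 20% of the anxious group's failures go unsignalled, and rises to 92.8% if instead 20% of the low-anxiety group's failures do.

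**4. Range with no true difference.** f from 30% to 50%, signalling 90-95% in one group v 60-85% in the other.
- Smallest false difference: 0.30 × (0.90 − 0.85) = 1.5 points.
- Largest: 0.50 × (0.95 − 0.60) = 17.5 points.
- Rejection is about nominal (5-6%) at 90% v 85%, and 26% at f = 50% with 95% v 60%.

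**5. Check on the mechanism.** With equal signalling of 90% in both groups, rejection stays at 4.8-5.5% for f of 30%, 50% and 70%. The false rejections come from the gap in signalling, not from under-signalling as such.

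**The case against.** The case on the other side has several parts, and most of it limits how far the point can be taken.

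- **A reader might infer that the plan counts every silent patient as a success and never asks for a score.** It does not say so. The classification of these patients is unstated; default success is the natural reading of the definitions, not a written rule.
- **A reader might infer that the two groups are measured by different procedures.** They are not. One instruction, one operator and one setting apply to all. What might differ is how patients respond to the instruction. The text also tells patients who feel pain to signal; it does not present signalling as optional.
- **A reader might infer that anxious patients do signal differently, or in a known direction.** The documents contain no evidence of this. The size of the effect rests wholly on assumed rates, and with a small gap the error rate hardly moves.
- **A reader might infer that nothing in the data could later address the problem.** That goes too far. The cold test is not triggered by a hand signal, and supplemental anesthesia is recorded. But the cold test does not measure pain during treatment, the plan does not say its result is recorded, and supplementation may itself follow a hand signal. These allow partial sensitivity checks only.
- **Any self-reported pain score depends partly on willingness to report.** This stands. A prompted score removes the dependence on the hand signal but not every reporting difference.

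What survives is that the plan schedules no pain score during treatment for all patients, and the factor that could affect the trigger is the one that defines the groups.

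**Conclusion.** The concern holds as a risk of measurement bias in the outcome named in the null hypothesis. As planned, a pain score during treatment exists only for patients who signal, and signalling could plausibly vary with anxiety. The direction and size are unknown.

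Under the assumed rates above, and if silent patients count as successes, the consequence runs from negligible (a 1.5-point false difference, rejection close to 5%) to serious (17.5 points and 26% rejection, or power roughly halved from 58% to 27-36%). This is a change the plan should make: it is inexpensive, and scores not collected during treatment cannot be recovered at analysis.

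**What to change.** 1. Keep the hand signal. In addition, have every patient mark the HP-VAS at the same fixed points of treatment (for example, end of access and end of instrumentation), whether or not a hand was raised.
2. Define success or failure from the highest mark made during treatment, up to and including the one at the first supplemental injection given during treatment. Apply the 55 mm boundary already used for eligibility.
3. State in advance how patients given additional anesthesia for a positive cold test before treatment starts are classified. Without this, a rule tied to the first additional injection could leave them with no mark to be classified by.
4. Record the cold-test result, and use it with the supplemental-anesthesia record in a sensitivity analysis described as partial.

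The cost is one or two extra marks per patient on a scale already in use, with a brief pause for each. Sample size and extra staff are not affected. Prompted scores reduce differences in pain reporting between the groups but do not remove them, and the report should say so.

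### Success is scored on pain during treatment only, so a patient made comfortable by anesthesia added after a positive cold test counts as a success; the plan needs a scoring and recording rule

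*Combined protocol and SAP*

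**What the plan says.** All references are to the combined protocol and SAP.

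- **Hypothesis (Null Hypothesis).** "Dental anxiety does not affect the success of mandibular anesthesia in the treatment of symptomatic irreversible pulpitis in mandibular molar teeth".
- **Planned anesthesia (Anesthesia Protocol).** Topical spray, then the inferior alveolar nerve block (IANB), then buccal and lingual infiltration, described as "Additional 1.8 ml injection performed 5 minutes after IANB".
- **Withdrawal (Block Failure Definition).** This rule turns on the lip, not the tooth: "If deep lip numbness is not achieved within 15 minutes, the block is considered failed and the participant is withdrawn from the study".
- **When pain is scored (Outcome Evaluation).** "During treatment, if the patient feels pain, they raise their hand, and the pain is marked on the HP-VAS".
- **Outcome categories (Outcome Evaluation).** "Successful anesthesia: No or mild discomfort" and "Failed anesthesia: Moderate or severe pain".
- **Supplements (Outcome Evaluation).** "If required, supplemental anesthesia (PDL or intrapulpal) will be administered and recorded".
- **Cold test (Outcome Evaluation, last line).** "Cold test will be performed 15 minutes after IANB. If positive, additional anesthesia will be given". The line gives no type of anesthetic, no scoring rule and no recording statement.
- **Analysis (Statistical Analysis).** A chi-square test relates anxiety level to the success rate. Added anesthesia is not mentioned.

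**The concern.** A positive cold test at 15 minutes means that the tooth still responds after everything in the planned regimen has been given. The plan then adds anesthesia and scores pain afterwards. If the patient is comfortable from then on, the literal definition records a success, although the planned regimen may not have been enough without the addition.

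The chi-square test on this outcome is the only test of the null hypothesis. If rescued patients are counted as successes, the reported success rate describes a mixture: planned anesthesia alone in some patients, planned anesthesia plus rescue in others. If they are counted as failures, it describes something else. The plan does not say which is meant, and if the choice stays open it could be made after the data have been seen.

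**Working it through.** **Plan's own figure.** The only related figure is the sample size, and this point does not dispute it. A two-sided t-test with effect size 0.8 and alpha 0.05 has power 0.791 at 25 per group and 0.807 at 26, which matches the stated 26 per group and 81%. The plan gives no success, failure, cold-positive or rescue rate.

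**Step 1: order of events.**

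| Time after IANB | Event | Section |
|---|---|---|
| 0 min | IANB | Anesthesia Protocol |
| 5 min | Planned infiltration | Anesthesia Protocol |
| up to 15 min | Lip numbness; if absent, withdrawal | Block Failure Definition |
| 15 min | Cold test; if positive, anesthesia added | Outcome Evaluation |
| treatment | Pain marked on the HP-VAS | Outcome Evaluation |

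No clock time is given for the start of treatment. The 15-minute wait for lip numbness and the cold test itself imply that it starts after the 15-minute mark.

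**Step 2: apply the definitions to one patient.** Numb lip, positive cold test, addition given, then little or no discomfort.
- The withdrawal rule does not apply, because the lip is numb.
- The pain definition gives success.
- The placement of the cold-test line under Outcome Evaluation allows a reader to treat the positive test as failure.
- The recording rule names PDL and intrapulpal supplements and follows the line on pain during treatment. It may or may not cover the cold-test addition. Even if it does, it does not say how to score the patient.

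**Step 3: effect on the success rate and on the group difference.** Let f be the share of a group who would have moderate or severe pain with planned anesthesia alone. Let q be the share of those who are made comfortable by the cold-test addition. If they count as successes:

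recorded failure = f × (1 − q)

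recorded difference = (f_high − f_low) − (f_high × q_high − f_low × q_low)

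The first line shows that recorded success rises whenever q is above zero. In the second, the correction term can take either sign. All rates below are assumptions, chosen only to show that:

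| Assumed case | Low anxiety | Higher anxiety | Difference |
|---|---|---|---|
| No rescue | 30% | 60% | 30 points |
| 40% of failures rescued in each group | 0.30 × 0.60 = 18% | 0.60 × 0.60 = 36% | 18 points |
| 10% of each whole group rescued | 30 − 10 = 20% | 60 − 10 = 50% | 30 points |
| 45% vs 20% of failures rescued | 0.30 × 0.55 = 16.5% | 0.60 × 0.80 = 48% | 31.5 points |
| Equal true failure of 45%; 40% vs 20% rescued | 0.45 × 0.60 = 27% | 0.45 × 0.80 = 36% | 9 points (true: 0) |

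The difference can shrink, stay the same, widen, or appear where there is none.

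**Step 4: the same check on the alternative scoring.** Let c be the share of patients who would have been comfortable anyway but are cold-positive. If every cold-positive patient counts as failed:

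recorded failure = f + (1 − f) × c

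- f = 30% vs 60%, c = 10% in both groups: 0.30 + 0.70 × 0.10 = 37% and 0.60 + 0.40 × 0.10 = 64%, a difference of 27 points.
- f = 45% in both groups, c = 10% vs 30%: 0.45 + 0.55 × 0.10 = 50.5% and 0.45 + 0.55 × 0.30 = 61.5%, a difference of 11 points where the true difference is 0.

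This scoring is cleaner in meaning, but unequal cold response can shift it too.

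**The case against.** **The plan does state a rule.** Pain defines success for every patient, without exception, so a cold-positive patient is scored on pain like anyone else. This largely stands as a reading of the text. It does not remove the problem, because that literal rule is the one that credits rescue to the planned anesthesia.

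**The hypothesis does not require the stricter outcome.** It speaks of mandibular anesthesia, not of the block plus infiltration alone, and nothing in the plan names a positive cold test as failure. This stands. Comfort regardless of rescue is a legitimate outcome if the plan declares it. A reader might infer that the literal scoring cannot answer the hypothesis; the documents do not go that far.

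**The additions may be recorded.** PDL and intrapulpal are the only supplement types named, the cold-test line names none, and the record form is not available. This stands in part. A reader might infer that the data will be lost; the text shows only that recording is not assured.

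**The effect is unknown.** This stands. A reader might infer a bias in one direction, or a definite loss of power, but the assumed cases above point in different directions. A reader might also infer that one re-scored patient would decide the trial. For example, 8 vs 16 failures of 26 gives p = 0.026 by uncorrected chi-square, and 8 vs 15 gives 0.051. That example starts at the threshold (Fisher's exact test already gives 0.0505 for 8 vs 16), and the same is possible for any binary outcome at this sample size. It is not evidence about the cold-test rule.

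**The stricter scoring has its own weakness.** This stands, as the last calculation under the working shows.

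**Conclusion.** The point holds as a gap in the outcome definition, and it should be fixed. Confidence is high for the text: the literal rule counts patients rescued after a positive cold test as successes, the placement of the line permits the opposite scoring, and neither the withdrawal rule nor the recording rule settles the matter. That the addition precedes pain scoring rests on reading treatment as starting after the 15-minute checks.

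The one firm consequence is that the overall success rate is raised to the extent that such patients occur and are counted as successes. By how much, and whether the comparison between anxiety groups moves up, down or not at all, cannot be determined from the documents. The illustrative percentages are assumptions and should not be cited as an expected effect.

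**What to change.** Change scoring and recording only. Who receives additional anesthesia, and what they receive, stays as written.

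1. **Record** for each patient the cold-test result and every additional or supplemental anesthetic given.
2. **State the primary scoring rule before data are seen.** Suggested wording: *Anesthesia is successful if HP-VAS stays below 55 mm throughout treatment and the patient receives no anesthesia other than the topical spray, the IANB and the planned buccal and lingual infiltration. A patient given additional anesthesia for a positive cold test counts as failed.* The 55 mm limit is the plan's own boundary between mild and moderate pain in the eligibility criteria. The infiltration must be named, because the plan also describes it as additional. Under this wording a PDL or intrapulpal supplement counts as failure too.
3. **Sensitivity outcome:** HP-VAS below 55 mm during treatment regardless of rescue.
4. **Report** cold-test results and rescue by anxiety group, so that readers can see whether either scoring was shifted by unequal cold response.

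If the sponsor prefers outcome 3 as primary, the plan should say so and state that it measures planned anesthesia plus rescue.

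**Cost.** A few sentences in the outcome section and two fields on the record form, with no change to care, visits or sample size. The downside is that cold-positive patients who would have been comfortable anyway count as failed. This lowers the success rate, may lower power, and may itself shift the comparison if cold response among comfortable patients differs between groups. The gain is an outcome with one stated meaning, not assured power.
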